8.1.10. Response Rate for GAIS

The aesthetic response rate based on GAIS assessment will be calculated considering the percentage of subjects that have been rated 'improved', 'much improved' or 'very much improved'.

Each subject's 'Response' for GAIS with regards to NLF will be assessed for both treatment groups, Princess® FILLER Lidocaine and Juvéderm® Ultra XC, in this split face design.

8.2. Primary Effectiveness Estimand and Analysis

The estimand for the primary effectiveness endpoint that is defined as a binary variable indicating the subject is alive and has a NLF-SRS response based on the independent blinded evaluating investigator live assessment using the NLF-SRS at Week 24 after initial treatment and relative to baseline assessments. NLF-SRS responder with regards to each specific NLF is defined as a subject with at least one grade improvement from baseline in NLF-SRS in that NLF. The shifts of the NLF-SRS grades (0 to 4) at Week 24 from baseline based on blinded independent evaluating investigator live assessment will be summarized for Princess® FILLER Lidocaine and Juvéderm® Ultra XC. A frequency table with the number and percentage of responders and non-responders at Week 24 will be presented for Princess® FILLER Lidocaine and Juvéderm® Ultra XC treatments. Additionally, summary of actual values and changes from baseline will be provided for Princess® FILLER Lidocaine and Juvéderm® Ultra XC treatments at all post-baseline timepoints.

8.2.1. Hypothesis Testing

The hypothesis to be tested for the estimand for the primary effectiveness endpoint is:

$$H_0: p_A - p_B \leq d_0 \quad \text{versus} \quad H_1: p_A - p_B > d_0$$

This document is confidential.

where, p_A is the response rate for Princess® FILLER Lidocaine, p_B is the response rate for Juvéderm® Ultra XC, and d_0 is the non-inferiority margin set at -10%.

A negative value for the difference $p_A - p_B$ indicates that the response rate of Princess® FILLER Lidocaine is lower than the response rate for Juvéderm® Ultra XC.

The hypothesis testing of non-inferiority for paired proportions will be tested using a 1-sided, McNemar type test at an alpha of 0.025 with a delta of 0.10 (10%). Princess® FILLER Lidocaine will be considered non-inferior to Juvéderm® Ultra XC if the lower limit of the 2-sided 95% confidence interval (equivalent to the 1-sided 97.5% CI) for the difference between the proportions is greater than -10%.

McNemar type test using a GENMOD procedure and taking into account of paired data will be used for testing the non-inferiority of the rate difference in paired proportions considering non-inferiority margin (-10%).

SAS code for comparison of paired proportions could refer:

```
ods output parameterestimates=paramest;
proc genmod data=indiv;
  class id treatment;
  model response (event='1')=treatment/dist=binomial link=identity;
  repeated subject=id;
  lsmeans treatment/diff cl;
  lsmestimate treatment/cl lower testvalue=-0.1 alpha=0.025;
run;
```

Above analysis and confirmatory testing will be repeated on PPS.

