14.2 Statistical Analyses

The PPS and the FAS will be both considered equally important for the primary analysis; the primary analysis will be performed with the FAS; if Princess® FILLER Lidocaine can be considered non-inferior to Juvéderm® Ultra XC according to this analysis, the sensitivity analysis based on the PPS can be considered confirmatory. Otherwise, this analysis has to be considered exploratory. Non-inferiority is demonstrated only if the results are consistent for both analysis data sets.

Page 105 of 133

15 Mar 2021

All effectiveness analyses will be conducted for the FAS and subsequently for the PPS . Safety analyses will be based on the SAF.

Effectiveness

The primary effectiveness outcome measure will be evaluated by means of a one-sided 95% confidence interval for the difference in paired proportions p_A - p_B . At this, p_A is the response rate for Princess® FILLER Lidocaine and p_B is the response rate for Juvederm® Ultra XC. Thus, a negative value for this difference means that the response rate of Princess® FILLER Lidocaine is lower than the response rate for Juvederm® Ultra XC. Princess® FILLER Lidocaine will be considered non-inferior to Juvederm® Ultra XC if the lower confidence limit exceeds the non-inferiority margin of -10% and thus if the null hypothesis H0: p_A - p_B \leq -10% can be rejected. In addition to this, the response rates for both treatment groups will be tabulated.

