14.3 Sample Size Calculation

The primary effectiveness outcome measure will be evaluated by means of a one-sided 95% confidence interval for the difference in paired proportions p_A - p_B . At this, p_A is the response rate for Princess® FILLER Lidocaine and p_B is the response rate for Juvederm® Ultra XC. Thus, a negative value for this difference means that the response rate of Princess® FILLER Lidocaine is lower than the response rate for Juvederm® Ultra XC. Princess® FILLER Lidocaine will be considered non-inferior to Juvederm® Ultra XC if the lower confidence limit exceeds the non-inferiority margin of -10%.

Further assumptions for sample size calculation:

- Response rate at week 24 for Juvederm® Ultra XC is 88%
- Response rate at week 24 for Princess® FILLER Lidocaine is 87%
- Proportion of subjects with response only in one nasolabial fold: 21.9% (88.0% * 13.0% + 87.0% * 12.0% = 21.9%)
- Proportion of subjects with response in both NLFs: 76.5% (88.0% * 87.0% = 76.5%)

The latter two proportions were calculated on the basis of the response rates for Princess® FILLER Lidocaine and Juvederm® Ultra XC assuming that the two NLFs of one subject are independent. Since there should be a concordant correlation between the two NLFs of one subject, this assumption is considered to be conservative.

Based on these assumptions, 222 subjects will be necessary in order to achieve a power of 90%. Sample size calculation was done using nQuery Advisor® 7.0. The result is based on 1600 simulations using the Newcombe-Wilson score method to construct the confidence interval.

15 Data Handling and Record Keeping

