2.7. Determination of Sample Size

The primary effectiveness outcome measure will be evaluated by the one-sided 95% confidence interval of the difference between paired proportions $p_A - p_B$. At this, p_A is the response rate for Princess® FILLER Lidocaine and p_B is the response rate for Juvéderm® Ultra XC. Thus, a negative value of this difference means that the response rate of Princess® FILLER Lidocaine is lower than the response rate for Juvéderm® Ultra XC. Princess® FILLER Lidocaine will be considered non-inferior to Juvéderm® Ultra XC if the lower confidence limit does not exceed the non-inferiority margin of -10%.

Further assumptions for sample size calculation:

- Response rate at Week 24 for Juvéderm® Ultra XC is 88%
- Response rate at Week 24 for Princess® FILLER Lidocaine is 87%
- Proportion of subjects with response only in one NLF: 21.9% ($88.0\% * 13.0\% + 87.0\% * 12.0\% = 21.9\%$)
- Proportion of subjects with response in both NLFs: 76.5% ($88.0\% * 87.0\% = 76.5\%$)

The latter two proportions were calculated on the basis of the response rates for Princess® FILLER Lidocaine and Juvéderm® Ultra XC assuming that the two NLFs of one subject are independent. Since there should be a concordant correlation between the two nasolabial folds of one subject, this assumption is considered to be conservative.

Based on these assumptions, 222 subjects will be necessary in order to achieve a power of 90%.

Sample size calculation was done using nQuery Advisor® 7.0. The result is based on 1600 simulations using the Newcombe-Wilson score method to construct the confidence interval.

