8.6. Other Secondary Effectiveness Endpoints and Analyses

8.6.1. GAIS Response Rate - Blinded Independent Evaluating Investigator

Aesthetic response rate based on blinded independent evaluating investigator assessment at Week 24 relative to Baseline using the GAIS. This endpoint will be analyzed descriptively presenting the response rate and one-sided 95% CIs using McNemar type test given in [section 8.2.1](#).

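### The SAP tests the primary endpoint at one-sided 0.025, but the 222-subject, 90% power claim holds only at one-sided 0.05, and SAP 2.7 states the success rule backwards

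*SAP*

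**What the plan says.** The two documents give three versions of the rule for the primary comparison.

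- **Protocol 14.2 and 14.3 (and the synopsis).** The endpoint is "evaluated by means of a one-sided 95% confidence interval for the difference in paired proportions", and the device is non-inferior if the lower limit exceeds -10%. That is a one-sided alpha of 0.05.
- **SAP 2.7.** It keeps the one-sided 95% interval but declares non-inferiority "if the lower confidence limit does not exceed the non-inferiority margin of -10"%.
- **SAP 8.2.1.** The hypothesis "will be tested using a 1-sided, McNemar type test at an alpha of 0.025 with a delta of 0.10 (10"%). Success is declared "if the lower limit of the 2-sided 95% confidence interval (equivalent to the 1-sided 97.5% CI) for the difference between the proportions is greater than" the margin of -10%. The sample SAS code also sets alpha to 0.025.

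On sample size, Protocol 14.3 states that "222 subjects will be necessary in order to achieve a power of 90"%, and SAP 2.7 repeats the figure. Both attribute it to 1600 simulations with Newcombe-Wilson score intervals. Both plan about 270 randomized and at least 240 evaluable subjects (Protocol 9.4, SAP 2.6).

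SAP Section 11 lists changes from the protocol's analysis. It mentions the estimands and the added intervals and p-values, but not the change of alpha. SAP 8.6 and 8.7 still report one-sided 95% intervals while referring to the method of 8.2.1.

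**The concern.** A pivotal trial needs one success criterion, fixed before unblinding. Here the interval level differs between the protocol and the SAP, and between two sections of the SAP. One SAP section also states the decision in the wrong direction: taken literally, SAP 2.7 would call the device non-inferior when the interval fails to exclude the margin.

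Two consequences follow. Some results would succeed under the protocol and fail under SAP 8.2.1, and settling which applies after the data are seen would be hard to defend. And the stated power belongs to a test the SAP no longer plans to run. The criterion also governs more than one comparison: the same method is used in all six steps of the testing hierarchy (primary and two key secondary measures, each on FAS and PPS).

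**Working it through.** **Inputs (Protocol 14.3, SAP 2.7).** Response 87% for the test device (p_A) and 88% for the comparator (p_B); independent folds; margin -10 points; N = 222; power 90%.

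**Paired model.**
- Test side only responds: 0.87 × 0.12 = 0.1044
- Comparator side only responds: 0.88 × 0.13 = 0.1144
- Discordant total: 0.2188, matching the documents' 21.9%
- Variance per pair: 0.2188 − 0.01² = 0.2187
- Distance from the assumed difference to the margin: −0.01 − (−0.10) = 0.09

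**Formulas (normal approximation).** Power = Φ(0.09 / √(0.2187/N) − z₁₋α). N for 90% power = 0.2187 × (z₁₋α + 1.2816)² / 0.09².

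**Reproducing the stated figure.** At N = 222 the standard error is √(0.2187/222) = 0.0314, and 0.09/0.0314 = 2.867.
- One-sided 0.05: Φ(2.867 − 1.645) = 88.9%. Simulating the Newcombe-Wilson limit (1,000,000 draws) gives 88.7%.
- The Monte Carlo standard error of 1600 simulations at 90% is √(0.9 × 0.1/1600) = 0.75 points, so 88.7% lies within ±1.5 points of 90%. The stated figure is reproduced at 0.05.
- One-sided 0.025: Φ(2.867 − 1.960) = 81.8%; Newcombe-Wilson 81.0%. The stated figure is not reproduced.

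**Power at the planned sizes.**

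| N | 0.05, Newcombe | 0.025, Newcombe | 0.025, normal approx. |
|---|---|---|---|
| 222 | 88.7% | 81.0% | 81.8% |
| 240 | 90.6% | 83.9% | 84.6% |
| 243 (270 × 0.9) | 90.8% | 84.4% | 85.1% |
| 270 | 93.3% | 87.9% | 88.5% |

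**N for 90% at 0.025.** 0.2187 × (1.960 + 1.2816)² / 0.0081 = 283.7, so 284; by Newcombe-Wilson simulation about 290.

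**Results on which the two rules disagree.** At N = 243 the standard error is √(0.2187/243) = 3.0 points. The lower limit clears -10% if the observed difference is above −10 + 1.645 × 3.0 = −5.1 points at 0.05, or above −10 + 1.960 × 3.0 = −4.1 points at 0.025. Anything between passes under the protocol and fails under SAP 8.2.1.

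**Direction.** SAP 8.2.1 sets H1 as p_A − p_B greater than -10% and requires the lower limit to be above it; the protocol agrees. Only SAP 2.7 is reversed. This does not enter the power figures.

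**The case against.** Four points can be made for the plan.

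1. **222 is a minimum, not the planned size.** Correct: 81% is the power at the number the documents attach to 90%, not at the number they intend to recruit. At the planned sizes it is 84% (240) to 88% (270).
2. **The FAS analysis keeps drop-outs as non-responders.** The FAS therefore stays near 270, and subjects missing on both sides become concordant pairs, which lowers the variance. At N = 270 and 0.025, Newcombe power is 89.9% with 5% missing and 91.8% with 10% missing. This holds for the FAS alone. But both documents require the PPS to agree, and joint power cannot exceed PPS power, which is about 84% at 240. With 270 in the FAS and 240 in the PPS, the joint figure is about 84%.
3. **Independence is described as conservative.** With an assumed within-subject correlation of 0.1, 0.2 or 0.3, Newcombe power at 0.025 is 84.7%, 88.2% or 91.6% for N = 222, and 87.1%, 90.4% or 93.5% for N = 240. The true power may well be higher than the figures above. But the documents give no correlation, and their 90% is stated under independence.
4. **The stricter alpha is safe, and the reversed sentence is plainly a slip.** Both are fair. Following SAP 8.2.1 does not inflate type I error, and its hypotheses and code make the intended direction clear. Neither point reconciles the two interval levels or updates the power claim.

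The intervals in SAP 8.6 and 8.7 concern exploratory endpoints and affect no confirmatory decision, so aligning them is incidental.

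**Conclusion.** The concern holds. The confirmatory test has two alphas (0.05 in the protocol and SAP 2.7; 0.025 in SAP 8.2.1) and, in SAP 2.7, a reversed decision rule. The claim of 90% power with 222 subjects fits 0.05 and is wrong for the test in SAP 8.2.1, where it is 81%. At that alpha, success on both FAS and PPS at the planned 270 and 240 has about 84% power. These figures rest on the documents' response rates, independent folds and the 10-point margin; positive correlation between folds would raise them. The loss of power comes entirely from the change of alpha. The reversed sentence is a separate wording error, but it sits in the success criterion and must be corrected before unblinding.

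**What to change.** - Use one rule in the protocol, SAP 2.7 and SAP 8.2.1: non-inferior if the lower limit of the two-sided 95% interval (one-sided 97.5%) is greater than -10%.
- In SAP 2.7, change the interval level accordingly and replace the reversed wording so that the limit must exceed the margin.
- Restate power at one-sided 0.025 under independence: about 81% at 222, 84% at 240 and 88% at 270. Preferably also give it by analysis set, with the joint FAS and PPS figure.
- Record the change of alpha in SAP Section 11.
- For consistency, make the intervals in SAP 8.6 and 8.7 two-sided 95%.

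The cost is SAP wording and a protocol clarification. No further subjects are needed; the stated power becomes less favourable.

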8.2.2. Homogeneity & Treatment Effect

In order to assess the homogeneity of the primary effectiveness outcome measure and of the treatment effect among the clinical investigational sites, a generalized linear model with treatment, site, and treatment-by-site interaction as fixed effects and random subject effects will be fitted.

The generalized linear regression model in SAS statements could refer:

```
ods output parameterestimates=paramest;
proc genmod data=indiv;
  class id treatment site;
  model response (event='1')=treatment site treatment*site
  /dist=binomial link=identity;
  repeated subject=id;
  lsmeans treatment/diff cl;
run;
```

Where response=1 defines a responder and response=0 defines a non-responder.

Small clinical investigational sites with less than ten subjects will be pooled and a two-sided alpha level of 15% will be used to test for a treatment-by-site interaction. In case that the treatment-by-site interaction is not statistically significant (at the alpha level mentioned above), the treatment-by-site interaction will be removed from the mixed model and the confidence interval for the difference in proportions will be derived from this mixed model adjusted for site effects.

This document is confidential.

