In order to assess the homogeneity of the primary effectiveness outcome measure and of the treatment effect among the clinical investigational sites, a mixed logistic regression model with treatment, site, and treatment-by-site interaction as fixed effects and random subject effects will be fitted. Small clinical investigational sites with less than ten subjects will be pooled and a two-sided alpha level of 15% will be used to test for a treatment-by-site interaction. In case that the treatment-by-site interaction is not statistically significant (at the alpha level mentioned above), the treatment-by-site interaction will be removed from the mixed model and the confidence interval for the difference in proportions will be derived from this mixed model adjusted for site effects. If the treatment-by-site interaction effect is statistically significant (at the alpha level mentioned above), the treatment difference is not interpretable in the model. In this case, the treatment difference in the main effect model without adding the interaction effect is tested and in addition, the treatment difference by site will be presented and observed heterogeneities will be evaluated.

Subjects with missing NLF-SRS grades at Baseline and/or at Week 24 will be considered as non-responders for the primary analysis. Since it is very unlikely that the assessment of only one NLF will be missing, presumably either no or both assessments will be available for one subject at a certain time point. Therefore, this imputation method will probably decrease the response rate in both treatment groups simultaneously. Due to the fact that the sample size calculation was based on rather high response rates (88% for Juvederm® Ultra XC and 87% for Princess® FILLER Lidocaine), lower response rates will make it more difficult to demonstrate

non-inferiority of Princess® FILLER Lidocaine and thus this approach is considered to be conservative. In addition to this approach, a complete case analysis (using the available data without any imputation), a best-case analysis (missing values for Princess® FILLER Lidocaine will be considered as a response, missing values for Juvéderm® Ultra XC will be considered as a non-response), a worst-case analysis (missing values for Princess® FILLER Lidocaine will be considered as a non-response, missing values for Juvéderm® Ultra XC will be considered as a response), and a tipping point analysis will be conducted as sensitivity analyses.

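### The site-homogeneity model in SAP 8.2.2 is described as mixed but coded as an identity-link GEE, and its 15% interaction test has no named statistic and can be miscalibrated at the planned response rates

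*SAP*

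**What the plan says.** Three descriptions of one analysis stand side by side.

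- **Protocol 14.2** plans "a mixed logistic regression model with treatment, site, and treatment-by-site interaction as fixed effects and random subject effects will be fitted". If the interaction is significant, the protocol tests treatment in the main-effects model, presents the treatment difference by site and evaluates the heterogeneity.
- **SAP 8.2.2, text**, calls the model a generalized linear model with "treatment, site, and treatment-by-site interaction as fixed effects and random subject effects will be fitted". If the interaction is not significant at a two-sided 15% level it is dropped, and "the confidence interval for the difference in proportions will be derived from this mixed model adjusted for site effects". Sites with fewer than ten subjects are pooled. The SAP says nothing about what follows a significant interaction.
- **SAP 8.2.2, code**, is PROC GENMOD with "model response (event='1')=treatment site treatment*site", "dist=binomial link=identity" and "repeated subject=id". The only other output requested is least-squares means for treatment.

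SAP Section 11 lists two changes from the protocol: the estimand approach, and confidence intervals or p-values for the remaining objectives. It mentions neither the change of model nor the change of link. There is no rule for a cell at 100% response, for a site with no discordant pair, or for non-convergence.

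**The concern.** The REPEATED statement fits a population-averaged model with a working correlation. It contains no random subject effect, so neither the SAP text nor the protocol describes what the code does. The code also requests no joint test of the interaction terms, although the 15% rule needs one.

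The second issue is sparse data. With treatment, site and their interaction in the model, each site-by-filler cell has its own fitted probability. At 87-88% response in cells of 23-27 folds, some cells may have every fold responding. The fitted probability is then 1, the binomial variance is zero, and the model sits on its boundary. A mixed logistic model separates at the same cell, so going back to the protocol's model does not remove the problem.

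At stake is the poolability check. It decides whether the interaction is dropped and the site-adjusted interval reported. A test that rejects too often would signal heterogeneity between sites that is not there.

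**Working it through.** **Inputs.** Response 88% (Juvéderm) and 87% (Princess), folds taken as independent: SAP 2.7. About 270 subjects, 10-12 sites, 23-27 per site, cap 54 (68 with sponsor approval): SAP 2.6. Pooling below ten subjects and the 15% test: SAP 8.2.2. Missing grades counted as non-response: SAP 6.3. Loss to follow-up about 5%: Protocol 9.3. The documents give no figure for the site model itself. Their discordant proportion reproduces: 0.88 × 0.13 + 0.87 × 0.12 = 0.2188, stated as 21.9%.

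**Step 1: chance of at least one 100% cell.** For k equal sites of n subjects it is 1 − [(1 − 0.87ⁿ)(1 − 0.88ⁿ)]ᵏ. For 10 sites of 27: 0.87²⁷ = 0.0233 and 0.88²⁷ = 0.0317, so 1 − (0.9767 × 0.9683)¹⁰ = 0.43. With 5% missing as non-response the rates become 0.87 × 0.95 = 0.8265 and 0.88 × 0.95 = 0.836.

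| Sites × subjects | No missing | 5% missing |
|---|---|---|
| 10 × 27 | 43% | 13% |
| 11 × 25 | 55% | 20% |
| 12 × 23 | 68% | 29% |

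With 10% missing the range is 3-10%. Uneven recruitment raises these figures. A single site of exactly ten, which is not pooled, has a chance of 1 − (1 − 0.87¹⁰)(1 − 0.88¹⁰) = 1 − 0.7516 × 0.7215 = 46%. Under assumed uneven layouts totalling 270, with smallest sites of 10-12, the chance is 80-95% with no missing data, 50-79% with 5% missing and 27-55% with 10%. The documents give no such layouts.

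**Step 2: what a 100% cell does.** The site's treatment contrast is the mean of d, where d = Princess response minus Juvéderm response, taking the values −1, 0 or 1. One filler at 100% still leaves d varying if the other filler has a non-responder. An identity-link GEE fitted in Python converged in every one of 150 data sets for each of two layouts. In about 70% of the data sets with a 100% cell, its Wald statistic differed by more than 1% from the one computed directly from the paired differences. SAS was not run.

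**Step 3: when the Wald test degenerates.** The variance of a site's mean d is zero if the site has no discordant pair. At fold correlation r the discordant proportion is about 0.2188 × (1 − r), so the chance that some site has none is 1 − {1 − [1 − 0.2188(1 − r)]ⁿ}ᵏ.

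| Sites × subjects | r = 0 | r = 0.3 (assumed) | r = 0.5 (assumed) |
|---|---|---|---|
| 10 × 27 | 1% | 11% | 36% |
| 11 × 25 | 2% | 16% | 46% |
| 12 × 23 | 4% | 23% | 58% |

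SAP 2.7 itself expects the two folds to be concordant, so r above zero is the planned case.

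**Step 4: size of the interaction test under homogeneity.** Simulation used equal sites, the same true rates at every site, a nominal 15% level and an empirical-variance Wald test, with trials containing a zero-variance site set aside.

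- Independent folds, no missing data: 21-23% rejection overall, and about 30-35% when a 100% cell is present.
- Independent folds, 5% missing as non-response: still about 21-24%, although 100% cells are rarer.
- ANOVA F-test on d: 14.4-15.6% in every layout tried, equal and uneven, r from 0 to 0.5, with and without 5% missing. It stays computable when one site has no discordant pair.

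**The case against.** The strongest reply has four parts.

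1. **A 100% cell is not the expected case under every reading of the plan.** This stands. A reader might infer that the model will probably hit the boundary and fail. But 10 sites of 27 give 43%, and equal sites with 5% imputed non-response give 13-29%. Only the uneven layouts go well above half, and those are assumptions.
2. **The test does not break down.** This largely stands. A reader might conclude that it becomes undefined at a 100% cell. It does so only when a site has no discordant pair; otherwise it is computable but miscalibrated.
3. **The miscalibration depends on a statistic the SAP does not name.** This also stands. The code is offered as an example. A score-type test on paired differences, simulated with no missing data, rejected 13.4-13.5% with independent folds and 9-11% at correlation 0.5. That makes an unnamed statistic a defect in its own right, because the size of the gate ranges from below 15% to well above it depending on a choice left open.
4. **Little hangs on the result.** This stands in part. Non-inferiority is decided by the unadjusted test in SAP 8.2.1, and the hierarchy in SAP 8 does not use 8.2.2. The site-adjusted interval comes from the model after the interaction is removed, so one filler at 100% in one site does not put that model on its boundary. Both fillers at 100% in the same site would: 1-3% of trials with independent folds, 5-12% at correlation 0.5, without missing data.

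None of this touches the disagreement between SAP text, SAP code and protocol, or the silence of Section 11.

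**Conclusion.** The point holds in two parts. First, on the documents alone, the model is misdescribed, differs from the protocol in type and link, omits the joint test its own rule needs, and is not declared as a change. Second, under the plan's rates and equal sites, an empirical-variance Wald version of the 15% test would reject about 21-23% of the time when sites are homogeneous and folds independent. It would have no valid variance for some site in 1-4% of trials with independent folds, rising to 36-58% at an assumed correlation of 0.5.

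The documents do not support saying that the analysis is more likely than not to fail, or that the primary conclusion is at risk. The effect is confined to the poolability check and to whether the site-adjusted interval is reported. The size figures rest on equal sites, common true rates across sites and an empirical-variance Wald statistic; behaviour of SAS at the boundary was not tested. The correction should be made before analysis.

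**What to change.** In SAP 8.2.2:

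- Test treatment-by-site homogeneity at the 15% level by comparing the mean of d across pooled sites, with an ANOVA F-test or a permutation test. Name the one chosen.
- Take the site-adjusted difference and its interval from the site-stratified mean of d: site means weighted by site size, with the variance summed over sites. No site variance is inverted, so a site with no discordant pair causes no failure.
- Keep a descriptive by-site table of response rates for each filler. The section also sets out to assess homogeneity of the outcome itself, which d alone does not show.
- Delete the references to random subject effects and to a mixed model.
- Restore the protocol's instruction for a significant interaction: main-effect test plus treatment differences by site.

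In SAP Section 11, list the change from the protocol's mixed logistic model.

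The cost is SAP wording and simpler code. No new data are needed, and the primary test is unchanged.
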